3.3.2 Duration of Therapy

In the first year of therapy, patients will receive therapy continuously for approximately 2 four week cycles. At the end of every 2 cycles during the first year, patients will receive an MRI and return to clinic for clinical evaluation. The frequency of MRI's is based on clinical practice at the Neuro-oncology department at UCSF for patients on active therapy. Upon re-evaluation, patients who have not experienced excess toxicity or disease progression will continue on protocol therapy.

In the second year of therapy, patients will receive therapy continuously for approximately 3 four week cycles. At the end of every 3 cycles during the second year, patients will receive an MRI and return to clinic for clinical evaluation. Upon re-evaluation, patients who have not experienced excess toxicity or disease progression will continue on protocol therapy.

After administration of RAD001 for 2 years, patients will receive an MRI and return to clinic for clinical evaluation. At that time, they will be offered the opportunity to continue treatment if they have not experienced excess toxicity or disease progression. Patients will continue to be followed at three month intervals if after two years they continue to take RAD001.

The study will be terminated for the patient if treatment is delayed due to toxicity greater than 28 days measured from the last dose of RAD001.

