3.4.1.3 Follow-Up Assessments

- Protocol Completion Assessment:
 - After administration of RAD001 for two years, patients will be offered the opportunity to continue treatment. There is no limit to the course of treatment an individual patient may receive. However, the patient will continue to be evaluated at 3 month intervals while on RAD001 and a decision to discontinue treatment after 2 years of therapy will be made on clinical grounds.
 - All patients must be observed for safety for 30 days following the last dose of RAD001 prior to withdrawal from study. This defines study completion.
 - Physical examination and comprehensive neurologic examination and grading, vital signs including weight, Karnofsky Performance status, all laboratory values, and MRI of the brain must be repeated within 2 weeks of the last day of study only if these have not been evaluated within 14 days, inclusive, prior to the date of withdrawal from study.
- Long-term Follow-up:
 - Patients will be followed according to routine clinical practice after removal from protocol therapy or until death, whichever occurs first.
 - Patients removed from protocol therapy for unacceptable adverse events will be followed until resolution or stabilization of the adverse event.
 - All patients will be followed for PFS and OS while on protocol therapy and while still receiving subsequent routine clinical care. Patients off protocol therapy will continue to be followed for PFS and OS only.

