3.4.1.4 Summary of Assessments

	Initial Screen	1-month Assessment	Assessments every 8 weeks (+3/-7days unless otherwise noted) for year 1 of therapy	Assessments every 12 weeks (+3/-7days unless otherwise noted) after first year of therapy	30 days after completing protocol therapy
Procedure:					
Clinical Evaluation	X		X	X	

Vital Signs	X		X	X	
Neurologic Exam	X		X	X	
Toxicity Check	X	X	X	X	X
Chest X-Ray	X		X Q 8 weeks (+/-7days)	X Q 12 weeks (+/-7days)	
Pulse Oximetry	X		X	X	
ECG	X				
Laboratory/ Diagnostic Tests:					
Serum pregnancy for women of child-bearing potential	X		X Q 8 weeks (+/- 3 days)	X Q 12 weeks (+/- 3 days)	
CBC with diff and platelets					
Chemistries					
Liver function tests					
Fasting cholesterol / triglycerides					
MRI of the brain	X		X	X	
Hepatitis B/C testing HBsAg, HBs Ab, HBc Ab Total, HBc IgM Ab and HCV antibodies	X		Patients who test positive for HBV antibodies without prior vaccination will be tested for HbsAg every 4 weeks (+/- 7 days) for re-activation		
Translational Research:					
Archival tumor tissue	X				
Study Drug:					
RAD001 starting dose:			10mg		

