Partial Response (PR): Greater than or equal to 50% decrease under baseline in the sum of products of perpendicular diameters of all measurable lesions. No progression of evaluable disease. No new lesions. All measurable and evaluable lesions and sites must be assessed using the same techniques as baseline. Responders must be on the same or decreasing doses of dexamethasone.

Partial Response, Non-Measurable (PRNM): Not applicable.

Stable / No Response (NR) / No Change (NC): Does not qualify for CR, PR, or progression. The designation of Stable/No Response requires a minimum of 8 weeks duration. All measurable and evaluable sites must be assessed using the same techniques as baseline.

Progression: 25% increase in the sum of products of all measurable lesions over smallest sum observed (over baseline if no decrease) using the same techniques as baseline, OR clear worsening of any evaluable disease, OR appearance of any new lesion/site, OR failure to return for evaluation due to death or deteriorating condition (unless clearly unrelated to this cancer).

Unknown: Progression has not been documented and one or more measurable or evaluable sites have not been assessed.

Best Response: This will be calculated from the sequence of objective statuses.

For patients with all disease sites assessed every evaluation period, the best response will be defined as the best objective status as measured according to the previously noted definitions. Best response is unknown if all objective status determinations before progression are unknown.

Neurological Exam: Although not used for determining response, it is useful to evaluate improvement in the neurologic exam that should coincide with objective measurement of tumor size.

+2 Definitely better
+1 Possibly better
0 Unchanged
-1 Possibly worse
-2 Definitely worse
(compared to baseline)

Time to Death: From date of registration to date of death due to any cause.

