6.1.2. Endpoint Definitions and Sample Size

The following definitions will be used for statistical analysis:

- Response: Response is based on the best response. The best response is defined as the best objective status as measured by the sum of products of perpendicular diameters of all measurable lesions.
- Progression-free survival: Number of days from the day the patient was enrolled to the day the patient experiences an event of disease progression or recurrence or to the date of death if disease progression or recurrence is not reached. All events of disease progression or recurrence will be included, regardless of whether the event

occurred while the patient was still taking drug or had previously discontinued study drug. All events of death will be included for patients who had not experienced disease progression or recurrence. If the patient does not have an event of disease progression or recurrence nor as the patient died, the patient's data will be censored at the date of last contact with the patient.

- Overall survival: Number of days from the day the patient was enrolled until the date of death. If the patient is lost to follow-up, the patient's data will be censored at the date of last contact with the patient.

For this single-arm phase II trial, the primary endpoint will be 6-month progression-free survival (PFS-6). Patients will be analyzed based on intention to treat. The primary determination of treatment success will be based on the results for those patients who are shown to still be low-grade. The intent is to perform the primary analysis at the time the 6 month PFS is known for all patients.

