6.1.4 Analyses Time-points and planned analysis

Primary end-point – 6-month PFS:

Analyses will be performed after all enrolled patients have completed 6 months on study drug, or whenever the progression status of all patients has been established, whichever comes first. The primary analysis will be based on Kaplan-Meier method. Kaplan-Meier estimates and the associated 95% CIs will be calculated for the 6-month PFS separately for low-grade glioma patients and secondary malignant glioma patients. The Cox proportional hazards model will also be used to allow for adjustment of the prognostic factors including age, KPS, extent of resection, and number of prior chemotherapy regimens.

Secondary end-point – overall survival and objective response rate:

The method described above for the analysis of PFS-6 will be applied to the analysis of OS. Response is based on the best response, defined as the best objective status as measured by the sum of products of perpendicular diameters of all measurable lesions. The point estimate and the associated 2-sided 95% CI for the response rate will be calculated separately for low grade and secondary malignant tumors.

Secondary end-point – biologic correlates:

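### PFS is censored at last contact, not last MRI, so a patient off drug who is in contact but unscanned counts as progression-free, which can raise PFS-6

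*Combined protocol and SAP*

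**What the plan says.** Section 6.1.2 defines PFS from enrolment to progression or death. Without either, the patient's "data will be censored at the date of last contact with the patient". Overall survival is censored at the same date.

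Progression is mainly an imaging event. Section 3.4.2.1 defines it as "25% increase in the sum of products of all measurable lesions over smallest sum observed (over baseline if no decrease"), clear worsening of evaluable disease, a new lesion, or failure to return because of death or deterioration.

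The scan calendar belongs to treatment. The table in 3.4.1.4 heads it "Assessments every 8 weeks (+3/-7days unless otherwise noted) for year 1 of therapy", and 3.3.2 says the MRI frequency "is based on clinical practice at the Neuro-oncology department at UCSF for patients on active therapy".

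Off drug, section 3.4.1.3 provides three things:
- "All patients must be observed for safety for 30 days following the last dose of RAD001 prior to withdrawal from study".
- One exit scan: "MRI of the brain must be repeated within 2 weeks of the last day of study only if these have not been evaluated" in the preceding 14 days.
- Then "Patients will be followed according to routine clinical practice after removal from protocol therapy or until death, whichever occurs first". PFS and survival continue to be followed, but no MRI interval is given.

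The primary analysis (6.1.4) is the Kaplan-Meier 6-month PFS. It is run after 6 months on drug for all, or "whenever the progression status of all patients has been established, whichever comes first".

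**The concern.** Last contact is the right censoring date for survival, because contact proves the patient is alive. It does not prove that a tumour is stable. A patient who stops for toxicity, has a clean exit MRI and is later only seen or telephoned has no further required occasion on which silent radiographic progression could be found. The plan nevertheless counts that patient as at risk and progression-free up to the contact, and through month 6 if the contact is that late.

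The direction is fixed. The Kaplan-Meier estimate is a product of terms (1 - d/n) over event times. Later censoring leaves each d unchanged and can only enlarge n, so every term stays the same or rises. The trial has one arm and its result is set against a fixed 17% (6.1.2), so no control group shares the bias. The documents do not say how PFS was censored in the source of the 17%.

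**Working it through.** **Design figure.** Inputs from 6.1.2: n = 40, null 17%, target 40%, one-sided alpha 0.05. Exact binomial: P(X>=11 | 17%) = 6.6% and P(X>=12 | 17%) = 3.0%, so the cut-off is 12/40 = 30%. Power at 40% is 92.9%, which agrees with the stated figure of over 90%. The hazard ratio is ln(0.40)/ln(0.17) = 0.517, also as stated. The design arithmetic is sound; the issue is the censoring date.

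**Exit MRI.** The last day of study is 30 days after the last dose and the scan falls within 2 weeks of it: 30 - 14 = 16 to 30 + 14 = 44 days after the last dose.

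**Hand example (assumed data).** All patients who stop have a clean exit MRI at day 30, no later scan, and contact beyond month 6.
- 4 stop and 6 of the other 36 are progression-free. Last contact: (4 + 6)/40 = 25.0%. Last MRI: 6/36 = 16.7%.
- 8 stop and 5 of the other 32 are progression-free. Last contact: (8 + 5)/40 = 32.5%, above the 30% cut-off. Last MRI: 5/32 = 15.6%.

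**Simulation (30,000-40,000 trials of 40 per scenario).** Assumptions: exponential progression with 17% progression-free at day 183; enrolment is day 1 of drug; scans at days 56, 112, 168, 224 and 280, each uniform in -7/+3 days; progression dated at the first scan after it occurs; stop times uniform over days 0-183; after the exit MRI no scan and no clinical detection; contact past month 6. The stopping shares are illustrations: 7% is the discontinuation rate in the renal cancer trial quoted in 3.2.5, and 20% is the plan's own stopping limit (6.1.1). About 60% of those liable to stop do so before progression is found: 0.6 x 2.8 = 1.7 patients at 7%, and 0.6 x 8 = 4.8 at 20%.

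*Baseline with no stops.* The week-24 scan falls on days 161-171 (mean 166), before day 183, so the estimate is about 0.17^(166/183) = 20.0%. This 3-point offset is separate from the censoring rule.

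*Per patient.* Someone who stops before progression is found counts as progression-free at day 183 with probability 67.4, 61.5 or 57.0% (exit MRI at 16, 30 or 44 days), against 33.3% if scanned on schedule. Each such patient adds (0.674 - 0.333)/40 = 0.9 to (0.570 - 0.333)/40 = 0.6 points.

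*Per trial, PFS-6:*

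| Liable to stop | Exit MRI (days) | Last contact | Last MRI, week 32 in | Difference (points) |
|---|---|---|---|---|
| 7% | 16 | 21.5% | 19.8% | 1.7 |
| 7% | 30 | 21.2% | 19.8% | 1.4 |
| 7% | 44 | 21.0% | 20.0% | 1.0 |
| 20% | 16 | 24.1% | 19.1% | 5.0 |
| 20% | 30 | 23.4% | 19.4% | 4.0 |
| 20% | 44 | 22.9% | 19.7% | 3.2 |

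At 10% stopping, last contact gives 21.5-22.1%. The chance of an estimate of at least 30% is about 9% with no stops, and 12-13, 13-16 and 18-24% at 7, 10 and 20% stopping.

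*Milder cases, last-contact rule (7% / 20% stopping):*
- Half of those who stop are scanned on schedule: 20.5-20.8% / 21.5-22.1%.
- In addition, half of the silent progressions are found clinically 30 days later: 20.4-20.5% / 20.9-21.2%.
- Last contact spread evenly from the exit MRI to one year: 20.8-21.0% / 22.2-23.1%.

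*Variant with a scan at month 6 (4,000 trials per scenario, nobody scanned after stopping).* This removes the baseline offset. Last contact gives 18.8, 19.7 and 22.3% at 7, 10 and 20% stopping; last MRI gives 16.7, 16.7 and 16.4%. The chance of reaching 30% is 6.1, 7.7 and 16.6%, against about 3% with full scanning.

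**The case against.** The plan has safeguards. Progression after stopping drug counts as an event, and patients off therapy are still followed for PFS (3.4.1.3). A visit with an unassessed site is classed as unknown, not stable (3.4.2.1). Sections 6.1.2 and 6.1.4 intend the analysis for when 6-month status is known. These show the intent, but none requires an off-drug scan and none changes the censoring date.

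The documents do not show that routine care omits MRI, and the headline case needs three things together: no later scan, no clinical detection, and contact past month 6. That stands. It is why the effect can be small or zero.

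The realistic shift may be modest. At 7% stopping it is at most 21.5 - 20.0 = 1.5 points over the no-stop baseline, against a binomial standard error of sqrt(0.17 x 0.83/40) = 5.9 points. At 20% the plan's own toxicity limit is reached, so that is a stress case. This also stands, but the error is one-sided and does not average out.

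Last-MRI censoring has its own weakness: it assumes that stopping is unrelated to progression risk. It also needs a rule for patients with no MRI after enrolment and a definition of an adequate scan. These points are right and are covered in the fix. Finally, the new censoring date does not supply the missing off-drug scans. Whether to require them is for the trial team, and the censoring sentence needs changing either way.

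**Conclusion.** The PFS censoring rule is wrong as written and should be fixed. It treats contact as evidence of no progression, and it can bias the primary estimate only upward. Under the headline assumptions it adds about 1.0-1.7 points over last-MRI censoring at 7% stopping and 3.2-5.0 points at 20%; milder assumptions give less. The effect is zero if no low-grade patient stops progression-free before month 6, if routine care scans those who do, or if last contact is the exit MRI itself. Direction is certain. Size is not, because neither stopping share is an estimate for this trial and the off-drug scan pattern is assumed.

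**What to change.** 1. **Section 6.1.2.** Write: *Patients without progression or death are censored at the date of the last adequate tumour assessment (MRI), including routine-care MRIs done off drug; a patient with no MRI after enrolment is censored at enrolment.* Define adequate by the rule in 3.4.2.1 that all measurable and evaluable sites be assessed. Keep last contact for overall survival only.
2. **Section 6.1.4.** Run the analysis once the week-32 MRI is in for every low-grade patient still on the scan schedule, so that a patient with a clear week-24 MRI remains at risk at day 183. If the team will not wait, state that PFS-6 is read at the week-24 visit. Either way, report that this scan precedes day 183 by 183 - 171 = 12 to 183 - 161 = 22 days. That favours the drug by about 3 points at a true 17%, and this fix does not remove it.
3. **Sensitivity analysis.** Count as failures the low-grade patients with no MRI at or after the week-24 window, and those who start another anticancer therapy before progression. In the simulation this gives 19.0-19.3% at 7% stopping and 16.8-17.9% at 20%.

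**Cost.** A few sentences, one table, the dates of routine-care MRIs, and an analysis up to 227 - 183 = 44 days later. Precision barely changes: at a true 40% the standard error is 7.8-8.1 points against 7.8 now. Changing the censoring date without waiting for week 32 would lower the estimate by about 0.5 points (20.1 to 19.6% with no stops), because 3-4 low-grade patients would lack that scan and about 0.7 (true 17%) to 1.5 (true 40%) of them would be progression-free but censored short of day 183. No treatment rule changes.

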3.2.2.1 Baseline Characteristics Inclusion criteria

- Patients must have a Karnofsky performance status of ≥ 60
- Patients must have a life expectancy > 8 weeks
- Patients must be ≥ 18 years old
- All patients must sign an informed consent document indicating that they are aware of the investigational nature of this study
- Patients must sign an authorization for the release of their protected health information
- Patients must have an MRI scan performed within 14 days prior to initial protocol treatment
- Patients must be registered in the UCSF Neuro-Oncology database prior to treatment with study drug
- Adequate bone marrow function as shown by: ANC $\geq 1.5 \times 10^9/L$, Platelets $\geq 100 \times 10^9/L$, Hb >9 g/dL
- Adequate liver function as shown by:
 - serum bilirubin $\leq 1.5 \times$ ULN
 - INR < 1.5 (Anticoagulation is allowed if target INR ≤ 1.5 on a stable dose of warfarin or on a stable dose of LMW heparin for > 2 weeks at the time of registration)
 - ALT and AST $\leq 2.5 \times$ ULN

- Adequate renal function: serum creatinine $\leq 1.5 \times$ ULN
- Fasting serum cholesterol $\leq 300 \text{ mg/dL}$ OR $\leq 7.75 \text{ mmol/L}$ AND fasting triglycerides $\leq 2.5 \times$ ULN. NOTE: In case one or both of these thresholds are exceeded, the patient can only be included after initiation of appropriate lipid lowering medication.

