3.2.2.2 Histologic Inclusion Criteria

- Patients must have histologically proven intracranial low-grade glioma at initial diagnosis. Low-grade gliomas include: astrocytoma, oligodendrogloma and mixed oligoastrocytoma. Pilocytic astrocytomas are excluded
- Patients must have unequivocal evidence for tumor recurrence or progression by histology as determined by review of pathology by an attending neuro-pathologist at UCSF
- If most recent histology shows progression to high grade glioma, patients must have had prior radiotherapy in order to be eligible
- Paraffin-embedded sections of tissue acquired from surgery at the time of suspected recurrence must be available for analysis

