3.2.2.3 Radiographic Inclusion Criteria

- Patients must have evidence for tumor recurrence or progression by MRI as determined by radiographic review of images by an attending neuro-oncologist or neuro-radiologist at UCSF
- If the steroid dose is increased between the date of the MRI and registration on the trial, a new baseline MRI is required. This MRI must be performed after ≥ 5 days on a stable or decreasing dose of steroids
- An MRI must be used throughout the period of protocol treatment for tumor measurement
- Patients must have evaluable disease

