Precise documentation of prognosis among recurrent low grade glioma patients treated with targeted therapy is limited in literature. A recent study based on the experience of the North American Brain Tumor Consortium (NABTC) was conducted to assess whether progression status at 6 months predicts survival from that time among recurrent high-grade glioma adult patients (Lamborn, Yung et al. 2008). In that study, it was reported that the estimated PFS-6 among recurrent grade III glioma patients who were not treated with temozolomide, a chemotherapy which is part of the standard of care for newly diagnosed gliomas, is approximately 17%. Since we expect patients with recurrent low grade gliomas to have better prognosis than grade III patients, we consider the lower threshold for the probability of 6-month PFS to be 17%. The calculation of sample size is based on a binary endpoint with the goal to increase 6-month PFS rate to 40%. This translates into a hazard ratio of 0.52 (experimental/historical). 40 patients will provide over 90% power using a one-sided test with alpha of 0.05.

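### The 17% PFS-6 null for the low-grade cohort is a recurrent grade III rate that the plan expects low-grade patients to beat, so rejecting it does not by itself show a drug effect

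*Combined protocol and SAP*

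**What the plan says.** Section 3.1 describes a single-arm, one-stage trial. The primary endpoint in section 6.1.2 is PFS-6, and "The primary determination of treatment success will be based on the results for those patients who are shown to still be low-grade".

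For the null, section 6.1.2 first concedes a gap in the evidence: "Precise documentation of prognosis among recurrent low grade glioma patients treated with targeted therapy is limited in literature". It then takes about 17% from a consortium analysis of recurrent grade III patients who did not receive temozolomide. It carries that figure over to the low-grade cohort on the ground that low-grade patients should have a "better prognosis than grade III patients, we consider the lower threshold for the probability of 6-month PFS to be 17" percent. The target is 40%. On the effect size the section says "This translates into a hazard ratio of 0.52 (experimental/historical"), and on the sample size "40 patients will provide over 90% power using a one-sided test with alpha of 0.05".

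Section 6.1.4 plans a Kaplan-Meier estimate of PFS-6 with a 95% CI, separately by grade, without naming the interval method. It adds a Cox model that adjusts for prognostic factors among the treated patients. No section states a numerical cut for success, a low-grade PFS-6 without effective drug, or a sensitivity analysis over other nulls.

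**The concern.** In a single-arm trial the null has to stand in for the missing control group. It should be the PFS-6 that the enrolled patients would have if the drug did nothing. Here it belongs to a different population, one that the plan itself regards as having a worse outlook. On the plan's own premise, then, 17% is not the no-effect rate for the cohort that decides success.

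Two features invite a reader to forget this. A one-sided 5% test is attached to 17%, and 17% is entered as the historical side of a treatment hazard ratio. Nothing else in the design separates drug from prognosis, because the Cox model compares treated patients with one another and supplies no comparator. A result that just excludes 17% could arise from low-grade prognosis alone and still be reported as activity of RAD001.

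**Working it through.** **Inputs from section 6.1.2:** n = 40, null 17%, target 40%, one-sided alpha 0.05, hazard ratio 0.52. **Assumed, because the documents do not give it:** the low-grade PFS-6 with no drug effect, p, shown over a range of 20% to 35%.

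**Step 1: reproduce the plan's figures.** Hazard ratio = ln(0.40)/ln(0.17) = 0.517, which matches 0.52. The stated value therefore uses 17% as the low-grade historical rate. For the exact one-sided binomial test, P(X ≥ 11 | 40, 0.17) = 0.066 and P(X ≥ 12 | 40, 0.17) = 0.030. The cut is 12/40 and the actual alpha is 3.0%. Power is P(X ≥ 12 | 40, 0.40) = 0.929, which agrees with over 90%. The arithmetic is sound; the question is what the null represents.

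**Step 2: allow for the planned interval.** If the decision rests on a two-sided 95% CI whose lower limit must exceed 17%, the cut depends on the method. With complete six-month follow-up, the lower limits at 12/40 are:

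- log-transformed Kaplan-Meier: 18.7%, so the cut stays at 12
- log-log: 16.8%, so the cut becomes 13
- exact: 16.6%, so the cut becomes 13
- plain: 15.8%, so the cut becomes 13

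With a cut of 13/40, power at 40% is 0.871. Both cuts are carried forward.

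**Step 3: find where the error passes 5%.** Solve P(X ≥ cut | 40, p) = 0.05 for p.

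- Cut 12: p = 18.3%. On the plan's hazard scale, ln(0.183)/ln(0.17) = 0.96, a hazard about 4% below grade III.
- Cut 13: p = 20.4%. Here ln(0.204)/ln(0.17) = 0.90, a hazard about 10% below grade III.

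**Step 4: chance that an inactive drug passes, by assumed no-effect rate.**

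| Assumed no-effect PFS-6 | Hazard ratio vs grade III, ln(p)/ln(0.17) | Cut 12/40 | Cut 13/40 |
|---|---|---|---|
| 20% | 0.91 | 8.8% | 4.3% |
| 25% | 0.78 | 28% | 18% |
| 30% | 0.68 | 56% | 42% |
| 35% | 0.59 | 79% | 69% |

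**The case against.** The best defence is that the plan is open about this. It names the source population, labels 17% a lower threshold and says the literature is thin. The primary objective is to determine PFS-6, the planned analysis is an estimate with an interval, and no passage says that excluding 17% equals success. A floor taken from the nearest available series is a common choice in a screening trial. All of that stands, and it limits the point to interpretation. It does not remove the point, because the same paragraph attaches a one-sided test to 17% and makes it the historical side of the treatment hazard ratio.

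A second defence is that eligibility may offset the better grade. Entry requires "unequivocal evidence for tumor recurrence or progression by histology" and "Patients must have evidence for tumor recurrence or progression by MRI". Any number of earlier relapses is allowed (section 3.2.2.4), and section 3.2.2.1 says "Patients must have a Karnofsky performance status of" at least 60. The documents speak of better prognosis and give no PFS-6 comparison. A no-effect rate only slightly above 17% is therefore possible, and at or below 18.3% (cut 12) or 20.4% (cut 13) the error stays within 5%. This also stands.

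A reader might go further and infer that the true false-positive rate is above 5%. The documents do not show that; it depends on rates they do not contain. A reader might also take 12/40 as the plan's success rule. It is only what the stated one-sided exact test implies, and three of the four interval methods checked give 13. Finally, section 1.1.3.4 cites one-year PFS of 39-76% in recurrent low-grade glioma. Those are small series of patients treated with temozolomide, so the figures cannot serve as a no-effect rate.

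**Conclusion.** The mismatch is real and comes from the plan's own wording: success is judged in low-grade patients against a grade III rate that they are expected to exceed. Rejecting 17% supports the statement that PFS-6 is above a grade III historical rate, and no more. The stated 0.05 is the error rate against that benchmark.

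Confidence is high that the null is not a low-grade no-effect rate. Confidence is low on how much this matters numerically. The error could stay within 5%, or be several times larger if the no-effect rate were 25% or more. The figures assume a binary endpoint with complete six-month follow-up and 40 patients. The point should be fixed, because it bears on the only determination of success and the minimum remedy is small.

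**What to change.** In section 6.1.2, keep n = 40 and the 17% test. State that rejecting 17% means PFS-6 exceeds the recurrent grade III historical rate and is not by itself evidence of drug effect in low-grade glioma. Name the cut or interval method to be used, and report the chance of rejection for that cut over a range of assumed low-grade no-effect rates, as in step 4. This needs no extra patients or data; the cost is a narrower claim.

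A further option applies only if a justified recurrent low-grade benchmark can be found and fixed before outcomes are reviewed: use it as the null and restate cut, target and power. Section 6.1.3 mentions site historical data on grade at recurrence, so the site is a natural place to look. The documents do not say whether a usable PFS-6 exists there, and it may not. Illustrations at n = 40 (exact, one-sided 5%), where the first target keeps the plan's hazard ratio (target = null raised to the power 0.517):

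| Null | Cut | Target at hazard ratio 0.52 | Power at that target | Power at 40% |
|---|---|---|---|---|
| 20% | 13/40 | 43.5% | 94% | 87% |
| 25% | 16/40 | 48.8% | 90% | 56% |
| 30% | 18/40 | 53.7% | 90% | 31% |

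Keeping the planned effect size on the hazard scale therefore holds power near 90%, while keeping the 40% target does not. Section 3.4.5.2 has investigators discussing each patient's results monthly. If outcomes have already been seen, the benchmark comparison should be presented only as supportive and its timing disclosed.
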